10.4. Medication Modification/Withdrawal Due to an Adverse Event

If a severe adverse reaction develops during therapy, the study medication should be discontinued, and the subject should be withdrawn from the study.

10.5. Medication Errors

A medication error is defined as any preventable event related to dosing instructions, product labeling, or packaging that causes or leads to inappropriate medication use or subject harm while the medication is in the control of the investigative site or subject. Medication errors which result in adverse events should be recorded and reported as adverse events. All other medication errors should be reported to the study Sponsor through the Medical Affairs department within 7 days of identification by the site.

11. DISCONTINUATION

11.1. Study Discontinuation

The study may be discontinued under the following circumstances:

1. The Sponsor reserves the right to discontinue the study at any time.
2. Adverse event listings will be produced for safety monitoring at least once every two weeks during recruitment. The data will be tested to determine if there are greater than 20% of the subjects who have had \geq Grade 3 adverse events considered by the Investigator to be possibly, probably or definitely related to the study drug (defined by the Toxicity Grading Scale Tables provided in [Appendix II](#)).

If greater than 20% of the subjects have at least one Grade 3 or Grade 4 adverse event considered to be possibly, probably or definitely related to the study drug by the study Medical Monitor, then the study must be stopped and the Institutional Review Boards, and FDA's Division of Anti-Infectives will be notified. All safety and activity data will be submitted to the FDA in a timely manner.

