My signature below constitutes agreement with this protocol. I am providing the necessary assurances that this study will be conducted by me and my staff according to all stipulations of the protocol, including all statements regarding confidentiality, and in complete accordance with all applicable regulations including current Good Clinical Practice guidelines and the ethical guidelines set by the World Medical Assembly ([Declaration of Helsinki](#), last amendment in Fortaleza, Brazil October 2013). Furthermore, my signature below indicates that source documents will be available for review by the Sponsor or their designated representative.

Principal Investigator Signature:

Principal Investigator

Date

Print name: _____

With the signature below, the Sponsor approves of this protocol.

Sponsor Signature:

The Romark Institute for Medical Research

Date

Print name: _____

SYNOPSIS

Title:	A Randomized, Double-Blind, Placebo Controlled Trial to Evaluate the Efficacy and Safety of Nitazoxanide (NTZ) for Pre- and Post-exposure Prophylaxis of COVID-19 and Other Viral Respiratory Illnesses (VRI) in Healthcare Workers and Others at Increased Risk of SARS-CoV-2 Infection
Study Number:	RM08-3007
IND Number:	149,166
Indication:	Pre- and post-exposure prophylaxis of COVID-19 and other VRIs
Design:	Multicenter, randomized, double-blind, placebo-controlled trial to evaluate the efficacy and safety of NTZ for pre- and post-exposure prophylaxis of COVID-19 and other VRIs.
Number of Subjects:	≥800 up to 4,000 as required to obtain 24 COVID-19 illnesses
Population:	Healthcare workers and others at increased risk of contracting SARS-CoV-2.
Randomization:	1:1 at the subject level
Study Dose and Administration:	Group 1 (NTZ): Two NTZ 300 mg tablets orally twice daily (b.i.d.) for 6 weeks. Group 2 (Placebo): Two placebo tablets orally b.i.d. for 6 weeks. All subjects will receive a B complex vitamin ([REDACTED]) one tablet twice daily to mask potential chromaturia that may be associated with NTZ.
Objective:	Evaluate the effect of NTZ administered 600 mg orally b.i.d. for 6 weeks in preventing symptomatic laboratory-confirmed COVID-19 and other VRIs compared to that of a placebo.

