3. STUDY DESIGN

The study will be a multicenter, stratified, randomized, double-blind, placebo-controlled trial to evaluate the efficacy and safety of NTZ for pre- and post-exposure prophylaxis of COVID-19 and other VRIs.

Subjects will be stratified according to their most likely location of exposure, which is a proxy for exposure to SARS-CoV-2 and other VRIs. The strata are:

- Emergency Department
- Intensive Care Unit
- COVID-specific Care Unit
- Walk-in Clinic
- Paramedics and other first responders (e.g., firefighter/EMT)
- Social Activities (3-5 per week)
- Social Activities (>5 per week)

Within strata, subjects will be randomized 1:1 to one of the following groups:

- Group 1 (NTZ): Two NTZ 300 mg tablets b.i.d. for 6 weeks
- Group 2 (Placebo): Two placebo tablets b.i.d. for 6 weeks

This study is expected to run from April 2020 through April 2021.

Rationale for important issues in the study design is described below:

- *Rationale for study design.* *In vitro* data suggest NTZ may be effective against the most common viruses associated with VRIs including SARS-CoV-2. Except for influenza, there are no drugs or vaccines commercially available to prevent VRIs, especially pandemic and outbreak strains of non-influenza viruses like SARS-CoV-2. In the case of influenza these drugs are limited to only the neuraminidase inhibitors for chemoprophylaxis and the vaccine has been demonstrated to be less effective in elderly patients. This study is designed to determine if a drug with broad-spectrum antiviral activity like NTZ can prevent VRIs.

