5.2. Baseline (Day 1, may be same day as screening evaluation)

At baseline, the following procedures will be carried out:

1. Collection of a nasopharyngeal swab sample using a single nylon flocced dry swab inserted into both nostrils for RT-PCR.
2. Collection of blood sample for laboratory safety tests and anti-SARs-CoV-2 antibodies.
3. Collection of a urine sample for routine urinalysis (appearance, glucose, protein and blood).
4. Review and recording of any concomitant medications.
5. Provision of an electronic symptom diary to subject and subject completion of baseline electronic diary under supervision and instruction of study site personnel.

6. Randomization and dispensing of study medication (medication assigned in sequential order).
7. Administration of the first dose of study medication with food (< 1 hour after food intake) and a B complex vitamin ([REDACTED]) under observation of Investigator or a member of Investigator's staff, and entry in the medication administration record.
8. Instruct subject regarding:
 - a. *Administration of study medication.* Subjects will be instructed to take the study medication (two tablets) twice daily with the morning and evening meals, approximately every 12 hours (< 1 hour after food intake, preferably a high-fat meal but at a minimum a cereal bar) and a B complex vitamin ([REDACTED]).
 - b. *Completion of subject diary.* Subjects will be instructed on completion of the electronic diary.
 - c. *Use of birth control.* Female subjects of childbearing potential, if sexually active, will be instructed to continue an acceptable method of birth control for the duration of the study and for 1 month post-treatment. Acceptable methods of birth control include a double barrier method, oral birth control pills, an IUD, or medroxyprogesterone acetate administered intramuscularly.
 - d. *Follow-up visits:* Subjects will be instructed on the study schedule and follow up visits at Week 3, Week 6 and Week 8.
 - e. *Seeking emergency care or contacting the study physician or nurse:* Subjects must be informed to seek emergency medical care or contact the study physician or nurse if they develop any of the following symptoms listed below during the full 8-week study and follow-up period.

CONTACT STUDY PHYSICIAN, IF:

- Trouble breathing including shortness of breath
 - Severe headache, stiff neck, confusion or excessive somnolence

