5.6. Week 8 Evaluation (+7 days)

Subjects will attend in-clinic visits at Week 8 and the following procedures will be performed:

1. Physical examination as warranted by the Investigator for any change from baseline.
2. Collection of blood sample for anti-SARs-CoV-2 antibodies.
3. Review and recording of concomitant medications.
4. Review and recording of adverse events/side effects and complications. Note that all adverse events and complications must be followed until their resolution or stabilization even beyond the 8-week study period.
5. Document any infections diagnosed during the follow-up period.

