2.4 Interim Analyses

Two interim data reviews and analyses will be scheduled and held promptly after the pertinent milestone has been reached. The first analysis will occur when 25% of the subjects have completed week 3. The first interim analysis will be a blinded analysis for drug safety only.

The second analysis will occur when 50% of the planned 24 COVID-19 cases have been reported (i.e., after 12 COVID-19 cases are reported). The second interim analysis will be for safety and potentially stopping the trial for futility. The Interim Data Review Plan will be included in the Independent Data Monitoring Committee (IDMC) charter.

Futility will be assessed via the efficacy of NTZ for the COVID-19 endpoint. The IDMC will recommend stopping for futility if the CMH test statistic for comparing the treatment groups on the COVID-19 endpoint is less than 0.179 (i.e., a p -value greater than 0.3278). The CMH test will be conducted for the sole purpose of evaluating futility; there will be no early stopping for efficacy. This bound was set using O'Brien-Fleming bounds for futility with overall $\alpha = 0.049$.

The IDMC will conduct the meetings in accordance with the IDMC charter. No efficacy analysis is planned and no allocation of α to the interim analysis is necessary.

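### The two-weekly adverse-event listing and its 20% check are scheduled only during recruitment, leaving the last-enrolled subjects' dosing and follow-up without a specified aggregate review

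*Protocol*

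**What the plan says.** Protocol 11.1, item 2, sets the schedule: "Adverse event listings will be produced for safety monitoring at least once every two weeks during recruitment". The next sentence is the check itself: "The data will be tested to determine if there are greater than 20% of the subjects who have had" an event of Grade 3 or higher judged at least possibly related to study drug. It has no timetable of its own, so it takes that of the listings. If the proportion exceeds 20%, "then the study must be stopped and the Institutional Review Boards, and FDA's Division of Anti-Infectives will be notified". That consequence carries no time limit.

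The durations that matter are these:

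- Treatment (Protocol 3): "Two NTZ 300 mg tablets b.i.d. for 6 weeks".
- Time on trial: Protocol 5.2 refers to symptoms arising "during the full 8-week study and follow-up period". Section 5.6 allows the Week 8 visit up to 7 days late.
- Adverse events (Protocol 5.6): "Note that all adverse events and complications must be followed until their resolution or stabilization even beyond the 8-week study period".

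SAP 2.4 schedules two other reviews. The first is blinded, for safety only, and is held when a quarter of the subjects have passed Week 3. For the second, which covers safety and futility: "The second analysis will occur when 50% of the planned 24 COVID-19 cases have been reported". Protocol 14 provides for an IDMC and leaves its procedures to the IDMC charter and the Medical Monitoring (Safety) Plan, neither of which is among the documents.

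**The concern.** Close of recruitment is the wrong end point for a safety listing in a trial where each subject is dosed for six weeks after enrolment. A subject randomized on the last day has the whole course ahead, yet the listing and check are no longer scheduled. The duty to stop remains open-ended while the test that would trigger it does not. Those two sentences of 11.1 need to be reconciled.

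The stake is the aggregate view of events that are severe but not serious. The prior exposure that the Protocol describes at this dose is mainly short: 2,686 subjects for 5 days (1.2.4) and 12 subjects for 7 days (1.2.2). Section 3 says that prior NTZ safety data support the 6-week duration, but it gives no figures. Experience in the later weeks of treatment is therefore worth collecting completely.

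**Working it through.** The documents give no figure to reproduce. The check is timeline arithmetic, with the scale taken under a stated accrual assumption.

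**1. Length of the gap.** Take the last randomization as week 0.

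- Dosing ends at week 6: 6 / 2 = 3 two-weekly reviews not scheduled.
- The last visit is at week 8: 8 / 2 = 4 reviews. With the 7-day allowance, 9 / 2 = 4.5 intervals.
- The 8 weeks include the 6. Time off drug is 8 − 6 = 2 weeks, or 3 with the allowance.

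**2. What the last scheduled listing can contain.** Post-baseline safety laboratory tests are scheduled at Week 3 (±7 days) and Week 6 (±2 days) (Protocol 5.5). The earliest dates are 21 − 7 = 14 days and 42 − 2 = 40 days after Day 1. When recruitment closes, nobody enrolled in the last 14 days has scheduled Week 3 results, and nobody enrolled in the last 40 days has scheduled Week 6 results.

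**3. How many subjects.** Assumption: uniform accrual over R weeks. R is not in the documents. The study is expected to run from April 2020 to April 2021, so R is varied from 26 to 52. A value of about 46 is what remains of a span of about 54 weeks after the last 8 are set aside. The share still dosing is 6/R and the share still on study is 8/R. Counts are dosing / on study.

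| R (weeks) | Still dosing | Still on study | N = 800 | N = 2,842 | N = 4,000 |
|---|---|---|---|---|---|
| 26 | 23.1% | 30.8% | 185 / 246 | 656 / 874 | 923 / 1,231 |
| 46 | 13.0% | 17.4% | 104 / 139 | 371 / 494 | 522 / 696 |
| 52 | 11.5% | 15.4% | 92 / 123 | 328 / 437 | 462 / 615 |

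Randomization is 1:1, so about half are on NTZ: at N = 2,842, about 328 (R = 26) to 164 (R = 52). Those still dosing have 6 / 2 = 3 weeks left on average. The dosing time still to come is (N/R × 18) / (6N) = 3/R of the total, or 11.5% to 5.8%.

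**4. Whether the scheduled interims cover the gap.** Neither is set for it. The first falls when 25% have passed Week 3. Enrolment runs as needed to reach 24 COVID-19 illnesses, up to 4,000 subjects (Synopsis). If the 24th case closes recruitment, the 12-case review has already been triggered. If the cap closes it, fewer than 12 cases would imply a pooled rate below 12 / 4,000 = 0.3%, against about 1.2% reported in Protocol 8.1.

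**5. Whether the lapsed check could change the outcome.** Let f be the share still dosing, r the proportion of earlier subjects who have had a qualifying event, and x the proportion of late subjects who come to have one. Crossing requires f·x + (1 − f)·r > 0.20.

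- R = 46 (f = 0.130), with every late subject affected (x = 1): r > (0.20 − 0.130) / 0.870 = 8%. With r = 5%, crossing is impossible.
- R = 52 (f = 0.115), x = 1: r > (0.20 − 0.115) / 0.885 = 9.6%.
- R = 26 (f = 0.231), r = 5%: x > (0.20 − 0.769 × 0.05) / 0.231 = 70%.

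A late crossing is unlikely at any of these accrual lengths.

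**The case against.** The case on the other side has four parts.

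- **The gap is read from silence.** Section 11.1 does not forbid later listings, the sponsor may stop the study at any time, and the IDMC charter and the Medical Monitoring (Safety) Plan may schedule further reviews. This stands as a limit: the finding is that these documents specify no aggregate review after enrolment closes, not that none will take place. The words *at least* in 11.1 do not help, because they qualify the frequency and not the period.
- **Subjects remain protected individually.** Serious events go to the sponsor within 24 hours, the investigator reviews moderate and severe events (10.2), diaries are checked daily (5.3), and Suspected ARI and unscheduled visits record adverse events. None of this ends with recruitment. It stands too, but it does not replace the aggregate listing. An ALT of 5.1 to 10 times the upper limit is Grade 3 in Appendix II and does not by itself meet the serious-event definition in 10.1.
- **The check would hardly ever trip late.** Step 5 confirms this. A reader might infer that a stop which would have spared subjects further dosing is likely to be missed. The documents' own figures do not support that.
- **The exposed group is smaller than it looks.** Half are on placebo, they have about 3 weeks of dosing left on average, and at R = 46 about 87% of subjects have already finished the course under two-weekly listings. This is right, and it keeps the point modest.

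**Conclusion.** The point holds as a cheap improvement to safety monitoring. Section 11.1 gives a stated schedule the wrong end point. About three to four two-weekly reviews are left unscheduled while about 23% to 12% of subjects are still dosing. Those shares rest on assumed uniform accrual over 26 to 52 weeks; back-loaded accrual would raise them. What is lost is mainly the aggregate listing of non-serious Grade 3 events in the last cohort, including those found at the Week 3 and Week 6 laboratory tests.

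Two stronger readings are tempting and should not be drawn. One is that the late data go unreviewed until database lock; neither document says so, and the charter and safety plan have not been seen. The other is that subjects face 6 weeks plus a further 8; the 8 weeks are counted from Day 1 and contain the 6.

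**What to change.** In Protocol 11.1, item 2, replace *during recruitment* with *until the last subject's last visit*, so that the existing listing and the existing check cover the whole dosing and follow-up period. The threshold, the grading and the consequence of crossing stay as they are. If the IDMC charter or the Medical Monitoring (Safety) Plan already schedules such reviews, a cross-reference in 11.1 would make that visible.

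The cost is about four more listings from data already in the EDC system, with no added visits, samples or subjects.

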10. ADVERSE EVENTS

The term “adverse event” is defined for purposes of this study as any unwanted physical, psychological or behavioral change experienced by a subject during the course of the study and after taking the first dose of study medication regardless of its severity or relation to the study. Adverse events may include symptoms, signs, unexpected worsening of pre-existing conditions, clinically significant changes in laboratory values, diseases and syndromes, and significant and unexpected failures of pharmacological action of other medications. Symptoms of VRIs (cough, sore throat, nasal obstruction, fatigue, headache, myalgia, feverishness) and complications of VRIs will not be reported as adverse events.

Adverse events will be recorded on the appropriate EDC forms throughout the study, and the severity of each adverse event will be graded on a four-point scale: mild, moderate, severe, or life-threatening (See [Appendix II](#)). The duration of the adverse event and relationship to the study drug will also be recorded. All adverse events must be followed until their resolution or stabilization even beyond the planned study period.

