5.2 Description of Safety Analyses

Adverse Events

Adverse events will be graded by the investigator according to the “Guidance for Industry: Toxicity Grading Scale for Healthy Adult and Adolescent Volunteers Enrolled in Preventive Vaccine Trials” as adapted in the Study Protocol. The investigator will also assess causality (relationship to treatment) as *Definitely related*, *Probably related*, *Possibly related*, and *Unrelated*. AEs will also be coded using the Medical Dictionary for Regulatory Activities version 23 or higher (MedDRA®). Treatment-emergent AEs (TEAEs), defined as any AE that occurs after a patient receives the first dose of the assigned study treatment, will be summarized by the number and proportion of patients reporting at least one occurrence of the AE. Frequencies and rates of each TEAE will be summarized by MedDRA preferred term within system organ class (SOC), by severity grade, and relation to treatment for each treatment group. The rate calculation will be based on the number of patients in the Safety population for the relevant treatment group.

Treatment emergent serious adverse events (TESAEs) will be summarized and displayed by frequency and rate by MedDRA preferred term within SOC.

A by-patient AE data listing of all adverse events including verbatim term, coded term, grade, and relation to study treatment will be provided.

Laboratory Tests

Clinical laboratory tests will be performed at the times prescribed in the protocol. The following clinical laboratory tests will be analyzed:

Hematology:

Hemoglobin, hematocrit, complete white blood count (total and differential), platelet count, random blood glucose, total cholesterol, HDL, LDL, and triglycerides.

Clinical Chemistry:

AST, ALT, GGT, alkaline phosphatase, bilirubin (total and direct), BUN, creatinine, sodium, potassium, and chloride.

Urinalysis:

Appearance, glucose, protein, and blood.

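### The two paragraphs of Protocol 11.1 count related Grade 3/4 events by different assessors: the two-weekly test uses the Investigator's causality, the mandatory stop the Medical Monitor's, and nothing links the two

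*Protocol*

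**What the plan says.** Protocol 11.1, item 2, sets the only numeric study-level safety stopping rule in the two documents. (The numeric bound in SAP 2.4 is for futility.) It has three parts.

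- **Data source.** "Adverse event listings will be produced for safety monitoring at least once every two weeks during recruitment".
- **Test.** "The data will be tested to determine if there are greater than 20% of the subjects who have had" Grade 3 or higher events "considered by the Investigator to be possibly, probably or definitely related to the study drug".
- **Action, in the next paragraph.** "If greater than 20% of the subjects have at least one Grade 3 or Grade 4 adverse event" that is "considered to be possibly, probably or definitely related to the study drug by the study Medical Monitor, then the study must be stopped", with notification of the review boards and the FDA.

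The list that contains this rule opens permissively: "The study may be discontinued under the following circumstances". Its item 1 lets the Sponsor discontinue whenever it chooses.

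On causality data, Protocol Section 10 provides for one item per event: "The duration of the adverse event and relationship to the study drug will also be recorded". Protocol 10.1 defines the four relationship categories without naming who applies them; it names the Investigator for severity. SAP 5.2 does name the assessor: "The investigator will also assess causality (relationship to treatment) as" one of the four categories. Its by-patient adverse event listing carries a single relationship item.

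**The concern.** A mandatory safety stop should give one answer from the data put in front of the people applying it. Here the quantity that is tested and the quantity that forces the stop rest on two people's judgements of the same events.

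Two things can follow if the text is applied as written:

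- The two-weekly test can be positive with no stop required, because the Medical Monitor has judged some of those events unrelated.
- The condition for a mandatory stop can be met while the two-weekly test is negative, because the Medical Monitor has judged related some events that the Investigator did not. A test on the Investigator's call alone would not detect this.

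The Protocol gives no consequence for a positive first test, no review step between the paragraphs and no rule for disagreement. What is at stake is whether the stopping rule can be applied, and later shown to have been applied, without ambiguity.

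**Working it through.** **Step 1: the two paragraphs side by side (Protocol 11.1)**

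| Element | Test | Mandatory stop |
|---|---|---|
| Cut-off | more than 20% of subjects | more than 20% of subjects |
| Grades | 3 or higher | 3 or 4 (the same set on a four-point scale) |
| Causality categories | possibly, probably, definitely | possibly, probably, definitely |
| Assessor | Investigator | study Medical Monitor |
| Stated consequence | none | study must be stopped |

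Only the assessor and the consequence differ.

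**Step 2: where each count could come from**

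- *Investigator's count.* SAP 5.2 assigns causality to the Investigator. Protocol Section 10 records one relationship item. Protocol Section 12 has source forms completed by site staff and signed off by the Investigator.
- *Medical Monitor's count.* Protocol 11.1 is the only place where a Medical Monitor assesses anything. Neither document gives a field, a listing column or a table for that assessment. The columns of the two-weekly listing are not specified anywhere.

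**Step 3: how much disagreement separates the two counts**

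The 20% cut-off comes with no derivation, so there is no figure of the plan's to reproduce. The documents give neither a related Grade 3/4 rate nor a rate of disagreement. The rates below are assumptions, used only to show scale.

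Inputs: 800 and 4,000 subjects (range in the Protocol synopsis) and 2,842 (expected sample size, Protocol 8.1). During recruitment the number would be smaller.

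Let k be the smallest count above 20%: k = floor(0.20 × N) + 1.

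- N = 800: k = 161
- N = 2,842: 0.20 × 2,842 = 568.4, so k = 569
- N = 4,000: k = 801

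If the Investigator-related count is n, the mandatory condition is not met once the Medical Monitor's count falls to k − 1. That takes a net n − (k − 1) subjects judged to have no related Grade 3/4 event. At N = 2,842:

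| Assumed Investigator rate | n | n − 568 | Share of n |
|---|---|---|---|
| 21% | 597 | 29 | 4.9% |
| 22% | 625 | 57 | 9.1% |
| 25% | 710 | 142 | 20.0% |
| 30% | 853 | 285 | 33.4% |

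The share hardly depends on N: at 21% it is 8 of 168 (4.8%) for N = 800 and 40 of 840 (4.8%) for N = 4,000. In general it is about 1 − 0.20/r for an Investigator rate r.

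The opposite direction works the same way. At an assumed Investigator rate of 19% (0.19 × 2,842 ≈ 540), a net 569 − 540 = 29 further subjects judged related by the Medical Monitor would meet the mandatory condition while the test stayed negative.

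Modest disagreement therefore matters only when the rate lies close to 20%; further away, the assessors would have to differ widely.

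**The case against.** The strongest reply is that 11.1 is a two-step rule: screen on the Investigator's call, then confirm on the Medical Monitor's. Only the second paragraph carries a consequence, and giving the decision to a central Medical Monitor is a legitimate choice. On that reading a positive test without a mandatory stop is the rule working as intended. The reading is possible, but the text does not state it, and it leaves the other direction open: a screen on the Investigator's call does not pick up events that only the Medical Monitor considers related.

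A reader might infer that the Medical Monitor's assessment exists nowhere in the trial's safety data, or that the two-weekly listing cannot show it. The documents do not support that. Protocol Sections 6 and 14 refer to a Medical Monitoring Plan that was not available and is a natural place for such an assessment. SAP 5.2 describes reporting for the final analysis, not the two-weekly output. The supportable statement is that neither the Protocol nor the SAP provides for recording or listing it.

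A reader might also infer that subjects would be left unprotected. That goes too far. The Sponsor can stop at any time (11.1, item 1), an independent committee monitors safety (Protocol Section 14), and both interim reviews cover safety (SAP 2.4).

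Finally, 20% looks remote. Protocol 1.2.4 reports that the commonest adverse event, whatever its cause, was chromaturia at 10.8%, and that fewer than 1% of subjects stopped therapy for adverse events. Of those 3,147 subjects, 2,686 (85%) received 600 mg twice daily for 5 days, against 6 weeks here, so this experience is reassuring but not decisive. It limits the weight of the point without making the two paragraphs agree.

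**Conclusion.** The point holds as an inconsistency within a safety decision rule. In the current text of Protocol 11.1 the count tested every two weeks is not the count that triggers the mandatory stop. The two are not linked, and disagreement is not addressed in either direction. The permissive opening of the list and the mandatory wording of the second paragraph add to the uncertainty.

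Its practical size is probably small. The counts part company on about 5% disagreement only if the Investigator-related rate is near 21%, and that rate is an assumption with no support in the documents. The conclusion rests on the Protocol and SAP alone; the Medical Monitoring Plan might supply the missing link. No endpoint, estimand or efficacy analysis is affected. It should be corrected because the rule is mandatory and the correction is cheap.

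**What to change.** Reconcile the two paragraphs of Protocol 11.1 in one of two ways:

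- use the same causality assessment for the two-weekly count and for the count that triggers the mandatory stop; or
- if two steps are intended, state them, including what follows a positive first step and how disagreement is handled when either assessor calls an event related and the other does not.

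In both cases, make sure that the governing assessment is recorded for each Grade 3/4 event and shown in the two-weekly listing. If the Medical Monitoring Plan already provides for this, a cross-reference in 11.1 is enough. Which assessor governs is for the sponsor and the committee to decide.

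The cost is about a sentence in 11.1 for a single count, slightly more for a two-step rule and, if the Medical Monitor's view is used, at most one extra field for Grade 3/4 events. The Protocol expected the trial to run to April 2021 and the SAP is dated April 2024, so recruitment may be over. In that case the study report should state which causality assessment each two-weekly review used and whether the other would have given a different answer.
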